Study Type	Project 4 Testing preliminary efficacy of a program to reduce barriers to community participation. Translational Trial Phase I Allocation: Randomized Intervention model: Parallel Assignment Primary purpose: Community reintegration
Date of First Enrollment	November 3, 2020
Target Sample Size	50
Recruitment Status	Project 4, closed to recruitment
Primary Outcome(s)	
Project 4 Testing Preliminary Efficacy of a Program to Reduce Barriers to Community Participation: We will test the working hypothesis that an adapted program, focused on resolving environmental barriers and building self-management skills in the home and community, will be feasible and superior to usual care for daily activity performance and participation outcomes. The hypothesis is based on our previous work,^{2,3} the work of others,⁴⁻⁶ and our unpublished preliminary data.
 
Aim 1. Determine the acceptability and feasibility of the adapted program. We will conduct a process evaluation⁷ of this intervention to evaluate the acceptability and feasibility and to aid in the interpretability of the trial. We will test the hypothesis that the adapted program will have high acceptability (80% retention), high fidelity by therapists (95% of elements and 90% of dose delivered), low safety risk (no increased rate of falls or health care use compared with control group), and high adherence (80% of modifications in use) at 6 months.
 
Aim 2. Estimate the magnitude of efficacy of the adapted program on the primary outcome of community participation (RNL) and on exploratory outcomes of daily activity performance and self-efficacy (I-HOPE) to select optimal end points for a large pragmatic trial. We will test the hypotheses that the adapted program is superior to usual care at 6 months on the primary and secondary end points.
 
Time Points of Interest: Baseline, 1 month

ORGANIZATIONAL STRUCTURE AND RESPONSIBILITIES

Principal Investigator:

[name], OTR/L

Responsibilities include: Managing the operations of the study, ensuring tasks are completed, ensuring compliance with quality-assurance requirements (e.g., human participant protection), preparing interim reports, and publication of study reports.

Study Coordinators:

[name], MSOT, OTR/L and [name], OTD, OTR/L

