The conceptual model of the intervention (Figure 3). The ICF describes the mechanism of the adapted program. PAwLTPD have a health condition that affects their body structure and function. The home and community environments of PAwLTPD pose barriers that prevent successful and safe performance of daily activities and participation. Intervening to remove barriers and enable PAwLTPD to use problem-solving strategies to overcome barriers will improve daily activity performance and participation outcomes. This conceptual model is empirically supported by our recent work exploring the role of environmental barriers in function.¹⁰¹

Baseline Home Visit (T1) for all Participants
Outcomes (primary endpoints described in Table 2) will be assessed by blinded evaluators at baseline and 6 months. Additional exploratory outcome measures are listed under the assessments section.

Baseline and 6-month follow-up assessments will be conducted in the home by a trained and certified rater blinded to group allocation. Follow-up assessments will be completed by a blinded rater who did not conduct the T1 evaluation, as new home modifications could reveal group assignment.

Intervention

The occupational therapists will deliver the final adapted program in each participant’s home and community. The essential elements include resolving barriers in the home and community and self-management skills to identify and resolve barriers. The intervention will target barriers in the home initially. Participants will identify target activities they want to address. Although problem areas addressed are participant-specific (tailored), the process to identify and address the problems is systematic and reproducible. All participants will receive identical intervention components (see Table 1).

Waitlist Attentional Control Treatment. The waitlist control group will receive the adapted program after the 6-month follow-up is completed. Participants in the waitlist control group will receive interview visits (equivalent in time by an occupational therapy graduate assistant). After the six-month follow-up has been completed, participants in this group will be contacted and asked to participate in a validity check. They will then be offered treatment at the end of the follow-up period.

Follow-Up Periods

[figure not shown]

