The new program will be iteratively piloted with 3-6 individuals living with a long-term physical disability. The pilot participants will identify potential problems with acceptability of the program structure or process and information delivered to the participant. The program will be iteratively revised until a final program is sufficiently ready to deploy in a larger sample.

Outcomes will be assessed by blinded evaluators at baseline and 6 months. Our goal is to optimize the design of future trials, so we will examine a series of measures to evaluate their utility in the trial setting. Baseline and 6-month follow-up assessments will be conducted in the home by a trained and certified rater blinded to group allocation. Follow-up assessments will be completed by a blinded rater who did not conduct the T1 evaluation, as new home modifications could reveal group assignment. We will also track falls on a monthly basis.

Assessments

Primary Outcomes

In-Home Occupational Performance Evaluation (I-HOPE): The I-HOPE will be used to measure current activity patterns of participants, identify activities that are difficult but important to them, and identify the environmental barriers that influence those activities (person-environment fit). The I-HOPE is a multi-step assessment that evaluates the performance of people doing 42 activities in the home. Using labeled pictures of each home activity (e.g., washing dishes, getting in and out of bed), participants identify and prioritize preferred activities for intervention and give a subjective performance, satisfaction, and self-efficacy score for each activity. A trained rater (e.g., OT) observes the participant perform the activity and quantifies the person-environment fit (or misfit). The instrument yields five subscales- the activity subscale [$\alpha = 0.78$ (6 items)]; performance subscale [$\alpha = 0.85$ (8 items)]; satisfaction subscale [$\alpha = 0.77$ (8 items)]; self-efficacy subscale [$\alpha = 0.90$ (10 items)]; and the environmental barrier subscale [$\alpha = 0.77$ (6 items)]. Intraclass correlation coefficients were calculated for the I-HOPE subscales on a sample of 10 participants, and scores ranged from .94 to 1.0 for raters.¹⁴¹

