Reintegration to Normal Living Index (RNLI): The RNLI is a disability-related quality-of life-instrument that will be used to measure participants’ satisfaction with their home and community participation and has been validated on a population of community-dwelling individuals with chronic conditions.¹⁴² Participants will read 11 statements relating to their monthly activity patterns and assign each one a score based on a 10-point ordinal scale with 1 indicating “does not describe my situation at all” and 10 indicating “fully describes my situation.” Participants will complete the RNL at home and return it by mail.

Westmead Home Safety Assessment (WeHSA)⁹³: The Westmead Home Safety Assessment will be used to identify the number of environmental hazards in all areas of the home (e.g., seating, bedroom, medication management) via 72 standardized categories. Each category is specified with explicit descriptors to qualify a given fall hazard with a score of 0 for absent and 1 for present. Total hazards are summed. A trained rater will complete the assessment at baseline and at the 6-month follow up.

Exploratory Outcomes

Health and Retirement Study¹ (HRS) Activity Supplement 2015: The Health and Retirement Study is a

longitudinal study designed to address important questions on the challenges and opportunities of aging. The activity supplement questionnaire will be used to provide descriptive information on activity participation. Modifications have been made to allow for additional qualitative responses describing barriers and limitations to activities.

Falls prevention strategy survey (FPSS): The FPSS is a self-report instrument addressing protective behaviors related to fall risk among adults.¹⁴³ Response options reflect the frequency with which the respondent engages in twelve different fall prevention behaviors behavior (never, sometimes, regularly).

Participation frequency, importance and self-efficacy: The participation frequency, importance and self-efficacy measure address four areas of participation: routines, recreation, responsibilities and relationships.¹⁴⁴ Twenty-five different activities are rated by the participant on a 1-5 Likert-type scale in the areas of frequency, importance, and self-efficacy to complete the activity.

Falls: Calendars reporting falls and health care utilization will be collected monthly via REDCap survey (using an automated system and/or in person).

Covariates

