Adherence. Adherence measures the participant's continued use of the implemented modifications. We will use the standardized approach of Cumming et al.¹⁴⁷ to calculate adherence as recommendations used/total recommendations. Interventionists will rate adherence with intervention at the final session by using the Prescription Log to track recommendations made, implemented and reasons that any recommendations were not implemented. Initial adherence will be a proportion of the number of recommendations implemented /recommendations suggested. Finally, we will determine the number of recommendations used/recommendations suggested at 6 months. Reasons for abandoning strategies will be examined using the Adherence Log, in which the participant will report on current level of use for each modification: very useful, somewhat useful, not at all useful, no longer use equipment. Any independence that was regained by improved sensorimotor performance will not count against the adherence rating.

Cost. The cost of the treatment will be measured by tracking cost of modifications and adaptive equipment for each participant. This will be tracked using the Invoice Form which includes both costs from the contractor as well as costs of any equipment ordered from a medical supply company or obtained from a community resource (medical equipment lending program). The total amount of money spent on each person will be tracked on this form.

Safety. To explore the safety of our study, we will measure the number of falls and the circumstances surrounding the falls with a self-report Fall Form used at the 6 month follow up visit. The rate and severity of the falls will be calculated using a standardized algorithm established by Tinetti, et al, 1988.¹⁴⁸ We will also track health care utilization for participants in both groups (# of emergency room and outpatient visits, # of hospitalizations, and number of days in therapy) using the Health Care Utilization Form.

Process Evaluation

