First, we will examine the distributional characteristics of study variables (outcomes, covariates). Basic descriptive statistics for each measure and the intercorrelations among study variables will provide a simple initial view of the sample characteristics (demographic and health-related variables). Second, we will determine whether participants are representative of the eligible population by comparing baseline sociodemographic characteristics (eg, age, gender, education) of the study population with those eligible to participate in the study but who declined to participate. Continuous variables will be analyzed with the appropriate parametric methods (eg, *t* test) to test for differences between the participants in the study and those who refused. Discrete variables will be analyzed with the appropriate nonparametric test (eg, chi-square test of association) to test for differences between the participants in the study and those who refused.

Next, we will use unpaired *t* tests and chi-square tests to compare baseline characteristics in the 2 groups for descriptive information (except when statistical assumptions are not met, in which case we may use Wilcoxon or Fisher exact tests). We will examine the process data before the efficacy analyses.¹⁷⁰ The goal of Aim 1 is to examine the feasibility of conducting a larger trial by conducting a process evaluation. We will conduct between-group comparisons of process end points collected at 6 months (eg, health care utilization rate, safety, dosage delivered, and adherence rate) using unpaired *t* tests or chi-square tests. We will compare the characteristics of patients that complete the assigned intervention to those who do not for differences in disability severity and comorbidities. Descriptive statistics will be used for costs per participant and adherence.

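### Aim 1 hypothesises no increase in falls or health care use, but the plan gives these comparisons only tests of difference and no confidence interval

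*Combined protocol and SAP*

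**What the plan says.** In the combined protocol and SAP, the study summary table (Primary Outcome(s), Aim 1) includes as a hypothesis "low safety risk (no increased rate of falls or health care use compared with control group", judged at 6 months. No margin or tolerable excess is attached.

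The Aim 1 paragraph of Statistical Analyses provides for "between-group comparisons of process end points collected at 6 months (eg, health care utilization rate, safety, dosage delivered, and adherence rate", by unpaired t tests or chi-square tests. The same section promises basic descriptive statistics for each measure. The documents contain no interval, bound or decision rule for the safety contrast.

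Falls and health care use are each recorded in two places. On the monthly side, Program Revisions says "We will also track falls on a monthly basis", and the falls entry under Exploratory Outcomes says "Calendars reporting falls and health care utilization will be collected monthly via REDCap survey". The Safety paragraph of Process Evaluation names a "self-report Fall Form used at the 6 month follow up visit" and goes straight on to say that fall rate and severity will be calculated by a cited algorithm. It also says "We will also track health care utilization for participants in both groups", on a Health Care Utilization Form.

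Adherence rate is in the list for between-group comparison. Two sentences later comes "Descriptive statistics will be used for costs per participant and adherence". The description of the control condition says "The waitlist control group will receive the adapted program after the 6-month follow-up is completed".

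**The concern.** A test of difference can show that a rate has gone up. Failing to reject does not show that it has not, and with arms this small the test will usually fail to reject even when there is a material increase. The stated hypothesis is the absence of an increase, so what bears on it is an estimate of the contrast and the range of values the data leave open. The plan asks for neither.

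What is at stake is a sentence in the report. Aim 1 is meant to inform a larger trial, and a statement that the program did not increase falls would carry into that decision with more weight than the data can give it.

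**Working it through.** **1. The plan's own figure.** Sample Size Calculations gives environmental barrier changes of 26.28 (SD 18.03) and 10.09 (SD 22.27), two-sided 5%, 80% power. The difference is 16.19. The root mean square SD is √[(18.03² + 22.27²)/2] = 20.26. Then n per arm = 2 × (1.960 + 0.842)² × 20.26² / 16.19² = 24.6, rounded up to 25, so 50 in total is reproduced (a Welch noncentral t calculation gives 79.0% power at 25 per arm). The trial is sized on barriers; no calculation addresses safety. At the 80% retention target of Aim 1, 20 per arm remain.

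**2. Assumed inputs.** The documents give no rate or dispersion for falls or health care use. The ranges below are assumptions: control mean per 6 months μ, and negative binomial dispersion k (0 is Poisson).

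| End point | μ | k |
|---|---|---|
| Falls | 0.5 to 1.5 | 0 to 2 |
| Health care visits | 2 to 8 | 0.5 to 2 |
| Hospitalizations | 0.1 to 0.3 | 0 to 2 |

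**3. Interval when the observed rate ratio is 1.0.** With full follow-up and equal arms, the upper 95% limit is exp{1.96 × √[(2/n)(1/μ + k)]} and the lower limit is its reciprocal.

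- Falls, best case, n = 25: √[0.08 × (1/1.5 + 0)] = 0.231; exp(1.96 × 0.231) = 1.57; interval 0.64 to 1.57.
- Falls, worst case, n = 25: √[0.08 × (1/0.5 + 2)] = 0.566; exp(1.96 × 0.566) = 3.03; interval 0.33 to 3.03.

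| Upper limit | n = 25 | n = 20 |
|---|---|---|
| Falls | 1.57 to 3.03 | 1.66 to 3.45 |
| Visits | 1.55 to 2.40 | 1.63 to 2.66 |
| Hospitalizations | 2.75 to 6.82 | 3.10 to 8.56 |

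So even with identical observed rates, no scenario excludes a 1.5-fold increase.

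**4. What the planned tests would miss.** Simulated power against a true 1.5-fold increase (40,000 trials per cell, two-sided 5%):

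| Test | n = 25 | n = 20 |
|---|---|---|
| t test, falls | 10 to 48% | 8 to 39% |
| Chi-square, any fall | 9 to 21% | 7 to 17% |
| t test, visits | 12 to 42% | 10 to 35% |
| t test, hospitalizations | 5 to 13% | 5 to 11% |

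As a second route, take an assumed control proportion of fallers of 20 to 50% and a true increase of 15 points. Exact chi-square power is 21 to 23% at 25 per arm and 14 to 19% at 20. With equal fall rates the t test's two-sided error is 4 to 5%, so for falls the test is sound; it answers a different question.

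**5. Is an interval workable at this size?** For falls, a negative binomial model with a log person-time offset was simulated with equal true rates, assuming 80% of participants have 6 months of data and 20% have 1 to 5 months. Coverage of the 95% interval was 93 to 97%. The upper limit fell below 1.5 in 10 to 36% of trials at 25 per arm and 10 to 30% at 20. The method is usable, but a firm verdict would be uncommon.

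**6. Rare events.** For hospitalizations at μ = 0.1, the chance that an arm has none is exp(−2.5) = 0.082 under Poisson with n = 25, so at least one arm is empty with probability 1 − 0.918² = 16%. With k = 2 the arm probability is 1.2^(−12.5) = 0.102, giving 19%. At n = 20 the same steps give 25% and 30%. A Wald rate-ratio interval cannot be computed in those trials.

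**7. Adherence.** Process Evaluation defines it as recommendations used over recommendations made. Controls receive interview visits and are offered the program only after the 6-month assessment, so by inference they have no denominator and the between-group test has nothing to compare. In the intervention arm, with an assumed SD of participant proportions of 0.15 to 0.30, the 95% half-width t × SD/√n is 6 to 12 points at n = 25 and 7 to 14 at n = 20.

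**The case against.** The best defence is that this is a pilot. Sample Size Calculations says outright that statistical significance is not the aim. The other Aim 1 criteria (80% retention, 95% of elements, 90% of dose, 80% of modifications) are benchmarks without intervals, and the safety criterion can be read the same way, as a comparison of observed rates. That reading is fair, but it favours an estimate with its uncertainty over a test, and bare observed rates still leave the uncertainty of the contrast unstated.

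Four stronger readings are tempting, and the documents do not support them.

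- A reader might infer that the investigators will declare safety from a p-value above 0.05. No section says so.
- A reader might infer that the source of the fall rate is undefined. The Safety paragraph attaches the rate to the 6-month Fall Form and names a form for health care use. The records are duplicated, and what is missing is a sentence saying which feeds the comparison.
- A reader might see a flat contradiction on adherence. The second sentence does not say that adherence will only be described, and a test and a description can coexist. The difficulty is the missing control denominator.
- A reader might see a participant-protection problem. The study is rated minimal risk, with semi-annual DSMB review and separate SAE reporting. The point concerns what the report may conclude.

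It is also true that every magnitude here rests on assumed rates, and that a count model is one choice among several. An interval for a difference in mean counts would meet the main point too.

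**Conclusion.** The point holds as a matter of reporting, and it rests on the missing interval alone. The only between-group output planned for falls and health care use is a test of difference, and at 20 to 25 per arm a non-significant result cannot support the hypothesis of no increase. Under the assumed fall rates, the 95% interval around an observed ratio of 1.0 at 25 per arm runs from 0.64 to 1.57 at best and from 0.33 to 3.03 at worst. Different true rates would move these limits, but within the ranges examined they would not change the conclusion. The adherence item is a wording correction that changes no result. Overall this is worth considering and is not a defect that threatens the trial.

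**What to change.** In the Aim 1 paragraph of Statistical Analyses:

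- Report the intervention versus control contrast for falls and for health care use with a 95% confidence interval, and base the safety statement on that interval, not on the test.
- State in advance that at N = 50 the interval is descriptive and will usually not exclude a moderate increase. A formal non-inferiority claim is out of reach: at assumed faller proportions of 20 to 50%, margins of 20 down to 10 points need about 63 to 393 per arm (one-sided 2.5%, 80% power).
- For falls, a rate ratio from a count model with a log person-time offset is suitable. For rare events such as hospitalizations, use an exact or difference-in-rates interval, because an arm may have no events.
- Say which record feeds the comparison. The monthly calendars are a reasonable choice for rates, with the Fall Form kept for circumstances and severity. If the calendars do not separate the types of health care use listed under Safety, take those counts from the Health Care Utilization Form and say so.
- Remove adherence from the between-group list. Report it in the intervention arm, by the plan's own formula, with a 95% interval against the 80% target.

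The cost is a few lines of SAP text and a small amount of extra analysis, with no new data collection. The price is a weaker safety statement that often gives no firm verdict. The falls model's interval can also fall slightly short of nominal coverage.

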The components and data sources of the process evaluation are presented in Table 4. We will conduct a process evaluation to understand the feasibility and to refine the components of the intervention in preparation for a definitive trial.¹⁶² We will monitor recruitment metrics for all eligible participants including demographic characteristics, enrollment status, and reason for decline. We will determine the fidelity of the intervention by determining whether the intervention was delivered as planned and calculating the dose of the intervention received by both groups (number of minutes and number of sessions delivered). Interventionists will rate adherence at last visit as the number of recommendations implemented per recommendations suggested.¹⁶³ Long-term adherence will be calculated as the number of recommendations used at 6 months per recommendations suggested. We will examine reasons for abandonment of strategies. Environmental modifications are not provided as part of standard care in the United States; therefore, reliable cost data are not available. We will track the cost of service provision (in the treatment group) to prepare for future cost-effectiveness studies. We will record occupational therapist time to provide services (direct and indirect). The hourly wage of the contractor will be estimated using wage rates for the St. Louis area as reported by the US Bureau of Labor Statistics.¹⁶⁴ All materials costs will be captured from invoices. Costs will be estimated from the payer perspective (eg, Medicare allowable will be used to estimate covered clinical encounters.)¹⁶⁵

Table 4. Process Evaluation Construct Data: Source and Form

Reach	Enrollment; retention*	Reason eligible not enrolled; recruitment rate; retention rate
Fidelity	Implemented per plan [^]	Session by session checklist of each component
	Dose delivered [^]	Minutes of treatment at each session; number of sessions
	Dose received [^]	Recommendations implemented/total recommendations
Adherence	Adherence to recommendations ⁺	Recommendations used/total recommendations at 6 months; cause of abandonment
Costs	Costs [^]	Final prescription and invoice (materials); treatment grid (time)

Notes: Data source *Recruitment coordinator; [^]Interventionist notes; ⁺ 6- and 12-month follow-up assessment.

Statistical Analyses

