The goal of Aim 2 is to test the hypothesis that the adapted program will result in greater improvements in participation and daily activity performance than control at 6 months after intervention. Mixed-model repeated-measures analysis of variance will be used for longitudinal analyses of variables measured at >2 time points (ie, Reintegration to Normal Living Index, I-HOPE). The focus of this analysis will be the significance of the interaction between group and time. Hypotheses will test for interactions in terms of the equality of changes over time in the 2 groups. Contrasts will be used in testing the null hypothesis that changes between 2 specific time points in one group are equal to corresponding changes in the group. I-HOPE scores will be analyzed with analysis of covariance with the 6-month value as the dependent variable and the baseline value as the covariate. For all analyses, we will determine whether required distributional and model-specific assumptions are satisfied. To explore the potential trial end points, we will select the best independent indicator of participation and compare the measures for sensitivity and statistical efficiency with data collected at 6 months after intervention.

Sample Size Calculations

Although statistical significance is not the goal of this study, we estimated a sample size using a power analysis for a 2-sided, 2-sample, unequal-variance *t* test using G*Power with a significance level of 5% and power of 80%.¹⁷³ The sample size calculation includes a correlation between baseline and follow-up measures and is based on analysis of change scores, which is equivalent in efficiency to the proposed analytic model. Data were used from a pilot study with a total of 113 community-dwelling older adults.¹⁰⁰ We estimated the sample size for the mechanism of action (reducing environmental barriers). Environmental barrier mean changes in intervention and control groups were 26.28 (SD 18.03) and 10.09 (SD 22.27), respectively. A sample size of 50 (25 in each group) is needed to provide 80% power.

Potential Benefits, Risks and Alternatives

Benefits

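### RNLI and I-HOPE get a model meant for more than two time points but are scheduled at two, and I-HOPE has two analyses with no rule for which counts

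*Combined protocol and SAP*

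**What the plan says.** In Statistical Analyses (Aim 2), a repeated-measures mixed model is planned for "longitudinal analyses of variables measured at >2 time points (ie, Reintegration to Normal Living Index, I-HOPE". The test of interest is the group-by-time interaction, that is, equality of changes in the two groups. The same paragraph then states: "I-HOPE scores will be analyzed with analysis of covariance with the 6-month value as the dependent variable and the baseline value as the covariate". RNLI has no corresponding ANCOVA. The paragraph closes with a plan to "compare the measures for sensitivity and statistical efficiency with data collected at 6 months after intervention".

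The visit sections describe two assessments. Under Baseline Home Visit (T1): "Outcomes (primary endpoints described in Table 2) will be assessed by blinded evaluators at baseline and 6 months"; Table 2 consists of RNLI and I-HOPE. Under Program Revisions: "Outcomes will be assessed by blinded evaluators at baseline and 6 months". Two other entries differ. The Primary Outcome(s) row of the summary table ends with "Time Points of Interest: Baseline, 1 month", although the hypotheses in that row are at 6 months. The note to Table 4 refers to a "6- and 12-month follow-up assessment", attached to adherence.

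Sample Size Calculations says that the calculation "is based on analysis of change scores, which is equivalent in efficiency to the proposed analytic model".

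**The concern.** Three things do not fit together.

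- The condition for using the mixed model (more than two times) is not met by the visit schedule for either measure it names.
- I-HOPE, listed among the primary outcomes in Table 2 and in the Assessments section, has two analyses and no rule for choosing. Whoever analyses the data could report the more favourable p-value.
- One stated purpose of Aim 2 is to choose end points for a larger trial. If RNLI is judged by the interaction test and I-HOPE by ANCOVA, I-HOPE can look more efficient because of the method and not the measure.

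RNLI, which Aim 2 names as the primary outcome, may also lose precision although its baseline value is collected anyway. The efficiency statement in the sample-size section can be true of only one of the two proposed models.

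**Working it through.** **Inputs from the protocol.** Two-sided 5% level and 80% power; environmental-barrier changes of 26.28 (SD 18.03) and 10.09 (SD 22.27); 25 per arm (Sample Size Calculations). Retention target 80% (Aim 1). **Assumed, because not given:** correlation rho between baseline and 6 months, 0.3 to 0.8; k = 6-month SD / baseline SD, 1 or 1.25.

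**1. The plan's own figure.** Difference = 26.28 − 10.09 = 16.19. SD = √((18.03² + 22.27²)/2) = 20.26. Effect = 16.19/20.26 = 0.80. The normal approximation gives 25 per arm, total 50, as stated. An unequal-variance t calculation gives 79.0% power at 25 per arm and 80.6% at 26. The stated N is reproduced.

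**2. What the interaction test is.** With two times, complete data and separate baseline means for each group, the interaction estimate is the difference in mean change. On one simulated data set (25 per arm), the mixed model and the change-score comparison both gave an estimate of 0.0127 with standard error 0.3055. Type I error is correct (5.0% to 5.2% in simulation).

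**3. Precision against ANCOVA, complete data.** In units of the baseline variance:

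- change score: 1 + k² − 2·rho·k
- ANCOVA: A = k²(1 − rho²)

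The difference is (1 − rho·k)², so ANCOVA gains unless rho·k = 1. Example, rho = 0.5, k = 1: 0.75/1.00 = 0.75. Example, rho = 0.8, k = 1.25: 0.5625/0.5625 = 1.00.

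**4. Precision with 80% followed up.** The mixed model also uses people with a baseline value only, so the ratio becomes A/(A + 0.8(1 − rho·k)²). Example, rho = 0.3, k = 1: 0.91/(0.91 + 0.392) = 0.70.

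| ANCOVA / interaction variance | rho 0.3 | 0.5 | 0.7 | 0.8 |
|---|---|---|---|---|
| Complete data, k = 1 | 0.65 | 0.75 | 0.85 | 0.90 |
| Complete data, k = 1.25 | 0.78 | 0.89 | 0.98 | 1.00 |
| 80% followed up, k = 1 | 0.70 | 0.79 | 0.88 | 0.92 |
| 80% followed up, k = 1.25 | 0.82 | 0.91 | 0.985 | 1.00 |

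Simulation that also counts the cost of estimating the slope at this sample size gives slightly smaller gains: 0.66–0.92 (k = 1) and 0.80–1.02 (k = 1.25) with complete data; 0.71–0.94 and 0.84–1.02 with 20 of 25 per arm followed up.

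**5. Two I-HOPE tests on the same data.** Simulation, 100,000 trials per setting, 25 per arm, complete data:

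| | rho 0.3 | 0.5 | 0.7 | 0.8 |
|---|---|---|---|---|
| Disagree on p<0.05, effect 0.80 SD of change, k = 1 | 15.6% | 12.8% | 9.4% | 7.5% |
| Same, k = 1.25 | 11.7% | 7.9% | 4.0% | 2.9% |
| No effect, at least one p<0.05, k = 1 | 7.9% | 7.2% | 6.8% | 6.6% |
| Same, k = 1.25 | 7.3% | 6.6% | 5.8% | 5.5% |

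With 20 completers per arm, disagreement is 20.1–9.5% (k = 1) and 14.7–4.0% (k = 1.25).

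**6. The efficiency statement.** By step 2, change scores are equivalent to the two-time interaction test. They are not in general equivalent to ANCOVA. With equal variances and the planning figures, 25 per arm gives about 79% power by change score, and about 93%, 89%, 85% and 83% by ANCOVA at rho 0.3, 0.5, 0.7 and 0.8. For ANCOVA the planned N is therefore conservative.

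**The case against.** The schedule is not beyond doubt. If the 1-month entry in the summary table describes a real RNLI and I-HOPE assessment, there are three times, the condition in the model sentence is met, and steps 2 to 4 do not apply as written. The planned contrasts between two specific times would also be redundant with only two. Or the condition may be a slip for two or more. Two times is still the better reading, because the visit section schedules the Table 2 end points explicitly. In every case I-HOPE keeps two analyses.

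The RNLI test is valid, and its precision loss depends on quantities the documents do not give. At k = 1.25 and rho 0.7 to 0.8 there is almost nothing to gain. That stands: for RNLI this is an improvement, not the correction of an error. An SD ratio below 1 would favour ANCOVA more (ratio about 0.50 to 0.64 at k = 0.8).

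Much of the disagreement in step 5 is the precision difference seen again. At k = 1 and rho 0.3, ANCOVA alone has 92.5% power, the change score 79.3%, and at least one is significant in 93.8%. The separate harm from choosing is the null rate of 5.5% to 7.9%, and it arises only if someone does choose.

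The trial is a pilot that says significance is not its aim, and Aim 2 calls the I-HOPE outcomes exploratory. But Aim 2 also states superiority hypotheses, the analysis text centres on the significance of the interaction, and an estimate too needs one named model.

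The plan does not say that RNLI and I-HOPE will be compared under different models. The mixing of method with measure is a risk the wording leaves open.

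**Conclusion.** The concern holds. The I-HOPE duplication and the conflict over time points follow from the text and need no assumption about rho. The mixed-model condition does not match the scheduled visits, and no section clearly provides a third RNLI or I-HOPE assessment.

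The sizes rest on assumed rho of 0.3 to 0.8 and an SD ratio of 1 or 1.25. On those assumptions, the RNLI interaction test gives up between none and about a third of the variance that ANCOVA would save. The two I-HOPE analyses give different answers on significance in about 3% to 16% of trials at the planning effect. Taking the better one raises the false-positive rate from 5% to at most about 8%. The efficiency statement is right for the interaction test and wrong in general for ANCOVA, but the error is on the safe side when variances are equal. This should be fixed; it does not invalidate the trial.

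**What to change.** 1. Reconcile the time points in the summary table, the baseline visit section, Program Revisions and the Table 4 note. Also state whether 6 months is counted from baseline or from the end of the intervention, since the analysis section refers to 6 months after intervention and home visits run over 8 weeks.
2. If RNLI and I-HOPE have two times, replace the mixed-model sentence with one model for RNLI and each I-HOPE score: ANCOVA of the 6-month value on group and baseline value, or a mixed model with baseline means constrained equal. Include race and sex, because the groups are balanced on them; expect only a small gain.
3. Report the adjusted difference with its 95% confidence interval, and use the same model for every measure in the end-point comparison.
4. Delete the second I-HOPE analysis. If unblinded results have already been seen, report both and label the choice post hoc.
5. Reword the sample-size statement: a calculation on change scores is conservative for ANCOVA when baseline and follow-up variances are equal.

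The cost is wording and a few degrees of freedom. Baseline values, race and sex are already collected. If the follow-up SD is clearly larger and rho is high, the precision gain is about zero, but having one named analysis still helps.
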